18.4 Estimated Creatinine Clearance rate (eCCr) using Cockcroft-Gault Formula

$$eC_{Cr} = \frac{(140 - \text{Age}) \times \text{Mass (in kilograms)} \times [0.85 \text{ if Female}]}{72 \times \text{Serum Creatinine (in mg/dL)}}$$

18.5 Table of Events

Evaluation	Days -21 to -1 (Baseline)	Phase I and Phase II All Cycles ^t (cycle = 28 days) Subjects in Phase II/Run-In period only: Please note cycle numbers will start over with 'Cycle 1' after initiation of ruxolitinib							End of Treatment ^q	Follow-up ^r
		Day 1	Day 2 ^x	Day 8 ^x	Day 9 ^x	Day 15 ^x	Day 16 ^x	Day 22 ^x		
Informed consent ^a	X									
Inclusion/exclusion	X									
Medical and disease history ^b	X									
Physical examination/BSA ^c	X	X ^s							X	
Vital signs ^d	X	X	X	X	X	X	X	X	X	
ECOG performance status	X	X ^s							X	
Pregnancy test ^e	X								X	
Electrocardiogram	X									
Echocardiogram, MUGA, or cardiac MRI ^f	X	X (prior to every 2 cycles)							X	
Hematology ^g	X	X ^s	X	X	X	X	X	X	X	
Coagulation ^h	X	X ^s								
Blood chemistries ⁱ	X	X ^s		X		X		X	X	
BNP ^w		X ^s								
Viral hepatitis panel ^v	X									
HBV DNA testing ^y	X									
Bone marrow ^j	X	(X)							X ^l	(X) ^r
Correlative studies (Blood and bone marrow) ^l	X			X ^l (Cycle 1 of ruxolitinib only; Blood only)				X ^l (Cycle 1 of ruxolitinib only day 20 -27)	X ^l	
Response assessments (SPEP/UPEP, IFE, SFLC) ^{k,u}	X	X							X	(X) ^r
Serum β2-microglobulin	X									
Assessment of plasmacytoma ^m	X	(X)							(X)	(X) ^r
Bone skeletal survey ⁿ	X	(X)							(X)	
Carfilzomib administration ^o		X	X	X	X	X	X			

Ruxolitinib administration ^o		Twice Daily days 1 – 28 Phase I all subjects. Phase II: Subjects with < PR following Phase II/Run-In period, subjects ≥ PR following Phase II/Run-In period who then subsequently progress, and subjects who proceed directly to Phase II/Ruxolitinib							
Dexamethasone administration ^o		X		X		X			
Concomitant medications ^p	X	=====→						X	
Adverse event monitoring		=====→						X	
Follow-up									X ^r

(X) only if clinically indicated

- a) All subjects must sign an IRB-approved informed consent document prior to enrollment and prior to any study related procedures.
- b) Medical History including demographics, prior and current medical illness and conditions (including baseline symptoms and toxicities), prior surgical procedures. Disease history includes date of initial diagnosis, stage and extent of the disease, Prior anticancer therapy (types and response), surgery and/or radiation including documentation of sensitive or refractory status, (refractory defined as documented disease progression during or within 60 days of completing the last anti-myeloma regimen), and documentation of Proteasome Inhibitor refractory disease status.
- c) A complete physical exam, including height (screening only) and weight, neurologic assessment and assessment for extramedullary myeloma will be conducted at screening, day one of each cycle and End of Treatment visit. A symptom directed physical examination will be conducted as needed during a cycle. Plasmacytomas that can be followed by physical exam are to be evaluated on day one of each cycle. Weight to be measured on day one of each cycle with calculation of BSA (Subjects with a BSA > 2.2 m² should receive a carfilzomib dose based on a 2.2 m² BSA). Dose adjustments do not need to be made for weight changes of less than or equal to 20% from baseline weight. Baseline symptoms and residual toxicity from previous therapy assessed within 14 days prior to initiation of therapy.
- d) Vital signs including blood pressure, pulse, respiration rate, temperature. To be performed prior to each carfilzomib infusion and as clinically indicated.
- e) For females of childbearing potential, a negative serum pregnancy test must be documented within 7 days and a negative urine pregnancy test within 3 days of C1D1. A female of childbearing potential (FCBP) is a sexually mature female who: 1) has not undergone a hysterectomy or bilateral oophorectomy; or 2) has not been naturally postmenopausal for at least 24 consecutive months (i.e., has had menses at any time in the preceding 24 consecutive months).
- f) Echocardiogram, MUGA, or cardiac MRI to be performed at baseline, every 2 cycles (within 5 days of Day 1), and end of therapy to calculate LVEF. Subjects who develop signs/symptoms of congestive heart failure at any point during the study are required to have an evaluation of LVEF measurements by ECHO, MUGA, or cardiac MRI, preferably by the same method used at screening. If echocardiogram, MUGA, or cardiac MRI is done within 2 months from End of Treatment visit, it does not need to be repeated.
- g) Hematology: hemoglobin, WBC with differential, and platelet count.
- h) Coagulation: prothrombin time (PT), international normalized ratio (INR).
- i) Blood chemistry: sodium, chloride, potassium, magnesium, phosphate, uric acid, BUN, glucose (fasting at baseline), ALT/AST (SGPT/SGOT), alkaline phosphatase, total protein, total bilirubin, albumin, serum creatinine, and estimated creatinine clearance by Cockcroft-Gault Equations (Appendix 18.4) calcium and lactate dehydrogenase (LDH). Creatinine clearance required on days of the cycle other than Day 1 may be calculated using the Day 1 weight of the current cycle.
- j) Bone marrow aspirate to be collected at screening for % plasma cells, morphology, standard karyotype, cytogenetics by FISH and biomarkers. Repeat for % plasma cells at the time of CR and/or progression. Screening timepoint only: If bone marrow previously collected for pathology evaluation as previously described within 21 days prior to initiation of study therapy, the pathology evaluation does not need to be repeated as part of the screening assessments. However, a bone marrow aspirate must be performed for correlative studies (see Footnote L for information on correlative studies).

- k) Serum or urine protein electrophoresis (SPEP, UPEP), serum and urine immunofixation (IFE) and serum free light chain (SFLC) assay. To be conducted prior to each cycle (within 7 days of Day 1) until documentation of initial disease progression. For cycles delayed ≤ 7 days, repeat evaluations are not required. If the start of a new cycle is delayed > 7 days a repeat disease evaluation must be performed prior to the subsequent cycle. Phase II/Run-In subjects who cross over to Phase II/Ruxolitinib only: Disease responses will be calculated from disease evaluation performed just prior to initiating ruxolitinib (a new baseline will be established).
- l) Blood and bone marrow samples will be collected for correlatives prior to study treatment initiation (collection is recommended after eligibility is established; baseline samples may be collected during screening or pre-treatment on C1D1); Cycle 1 of ruxolitinib, between Day 20-27; and at disease relapse or progression after ruxolitinib has been initiated. Blood only will be collected on C1D8 of ruxolitinib. These correlative labs include serum cytokines panel, peripheral blood mononuclear cells (PBMC) for proteasome inhibition, and PBMCs for JAK inhibition. Approximately 28 mLs of blood will be collected (please refer to the Correlative Guidelines for the type of tubes required) and will be sent to the LCI HOT lab. A minimum of 12 mL (first or second pull permitted) of bone marrow aspirate will be collected and sent to the LCI HOT lab. Note: ruxolitinib must have been initiated to collect correlative samples post-baseline (do not collect post-baseline correlative samples on subjects receiving study treatment in Phase II/Run-In period). Every effort should be made to collect post-baseline correlative samples prior to carfilzomib and dexamethasone administration; after the morning ruxolitinib dose and before the afternoon dose of ruxolitinib. Correlatives collected during screening do not need to be re-collected in the event that the screening period extends beyond 21 days.
- m) Known or suspected plasmacytomas are to be assessed at baseline, as clinically indicated and to confirm response and/or progression. FDG-PET is not required but suggested. The same method of evaluation should be used throughout the study (CT/MRI/PET). Phase II/Run-In subjects who cross over to Phase II/Ruxolitinib only: For subjects with plasmacytomas present at screening, imaging using the same modality utilized at screening will be repeated prior to initiating ruxolitinib (a new baseline will be established).
- n) Skeletal survey includes plain X-rays of (including skull, all long bones, pelvis and chest) required if previous survey >12 weeks from study entry and at any time when clinically indicated.
- o) See section 5 for complete details on study drug administration, dose modifications and start of a new cycle of therapy.
- p) Concomitant medications and procedures: - all procedures and medications within 14 days prior to first dose until 30 days after the last dose.
- q) End of Treatment visit should be completed within 30 days of last dose of study drug with evaluation of safety at 30 days or prior to initiation of subsequent therapy (whichever comes first)
- r) Subjects who received ruxolitinib on study and discontinue therapy for reasons other than disease progression should continue to have disease assessments per standard of care done until progression or start of subsequent therapy. At such time, follow-up for overall survival status will take place every three months ± 7 days until death, lost to follow-up, or until the criteria defined for the final analysis (Section 13.4.1) are reached. Follow-up beyond the safety follow-up period is only required for subjects who received ruxolitinib. Follow-up may be completed by phone contact. Death information from public sources, e.g. death registry, obituary listing, etc. can also be used when it is available and verifiable
- s) C1D1 procedures do not need to be repeated if the screening procedure occurred within 5 days (this applies to C1D1 following screening; does not apply to C1D1 of Phase II/Ruxolitinib in subjects who cross over from Phase II/Run-In); Day 1 procedures for subsequent cycles do not need to be repeated if done within 3 days of Day 1.
- t) ± 3 day window permitted for holidays/administrative reasons
- u) Phase II/Run-In period only: Beginning with Cycle 1, disease evaluation results to assess response should be available for investigator review prior to dosing on Day 1 of each cycle (within 7 days of Day 1) until initiation of ruxolitinib (after ruxolitinib has been initiated, disease evaluation assessments will continue to be collected prior to dosing on Day 1, but results will not be required to be available prior to Day 1 dosing). Cycle numbers start over with the initiation of ruxolitinib and a new disease response baseline will be established.
- v) Viral hepatitis panel including HBsAg, HB core antibody, HB surface antibody, Hep C antibody and HIV at baseline only.
- w) BNP to be done Day 1 (± 3 days) of every cycle.

- x) A +/- 1 day window is allowed for study treatment on Days 2, 8, 9, 15, and 16 and procedures on Day 22, unless otherwise noted. All procedures required for Days 2, 8, 9, 15, and 16 should be performed within 1 day of study treatment, unless otherwise noted.
- y) For subjects with serologic evidence of resolved HBV infection (i.e. positive anti-HBs or positive anti-HBc) at Screening. HBV DNA testing by PCR must be performed locally. Subjects with serologic findings suggestive of HBV vaccination (Anti-HBs positivity as the only serologic marker) and a known history of prior HBV vaccination do not need to be tested for HBV DNA by PCR.

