6.3 Dose Modification Guidelines for Carfilzomib and Ruxolitinib during a Cycle of Therapy

Hematologic Toxicity	Recommended Action
-----------------------------	---------------------------

 • Grade 3^a or 4 Neutropenia (ANC < 1000 mm³) • Grade 4 Thrombocytopenia (Platelets < 25,000 mm³) or any grade with bleeding. 	
 • Withhold ruxolitinib and carfilzomib and re-evaluate in one week • If recovered to Grade 1 or better before next scheduled dose, continue ruxolitinib and carfilzomib at same dose level. • If recovered to Grade 2 neutropenia or Grade 3 thrombocytopenia, reduce ruxolitinib and carfilzomib dose by one dose level. Reductions in one drug and not the other may be considered with alternating dose reductions for subsequent occurrence. • If tolerated, the reduced dose may be escalated to the previous dose at the discretion of the physician.
Non-Hematologic Toxicity	Recommended Action
Cardiac Toxicity Grade 3 or 4, new onset or worsening of: 
 • congestive heart failure; • decreased left ventricular function; • or myocardial ischemia 	
 • Withhold carfilzomib until resolved or returned to baseline. • After resolution, consider restarting carfilzomib at a reduced next dose level if appropriate. • If tolerated, the reduced dose may be escalated to the previous dose at the discretion of the physician.
Pulmonary Hypertension	
 • Withhold carfilzomib until resolved or returned to baseline. • Restart at the dose used prior to the event or next dose level at the discretion of the physician. • If tolerated, the reduced dose may be escalated to the previous dose at the discretion of the physician.
Pulmonary Complications 
 • Grade 3 or 4 	
 • For drug related Grade 3 or 4 pulmonary toxicity, permanently discontinue carfilzomib.

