8.3 Screening Procedures

All screening procedures must be completed within 21 days prior to start of study treatment unless otherwise specified in the Table of Events (Appendix [18.5](#))

- Informed consent
- Inclusion/exclusion
- Medical and disease history
- Physical examination
- Vital signs
- ECOG performance status
- Pregnancy test for females of child bearing potential
- Electrocardiogram (ECG)
- ECHO, MUGA, or cardiac MRI
- Concomitant medications - all on-going medications and those taken within 14 days prior to first dose of study treatment
- Disease Assessments (see section 8.4.1)
- Laboratory Assessments (see section 8.4.2)

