13.4.3 Safety Analyses

Treatment administration will be summarized descriptively in terms of cumulative dose administration and dose intensity of ruxolitinib (adjusting for dose delays and reductions). Additionally, the relative dose intensity will be calculated in terms of the actual dose intensity as percent of the intended dose intensity. The maximum grade for each type of adverse event will be recorded for each subject and treatment-emergent adverse events (TEAEs) will be identified. TEAEs are defined as follows:

- An adverse event that occurs after treatment start that was not present at the time of treatment start; or
- An adverse event that increases in severity after treatment start if the event was present at the time of treatment start.

TEAEs will be summarized using frequencies and proportions, and these will be reviewed to determine patterns. Additionally, the relationship of the adverse event(s) to the study treatment will be taken into consideration.

Clinical laboratory tests (hematology, chemistry, coagulation panel, BNP), vital signs, and ECHO/MUGA/cardiac MRI (ejection fraction (%)) will be summarized with descriptive statistics.

Phase II Stopping Rule

It is estimated that the composite rate of Grade 3/4/5 AESIs (as defined in Section 13.2.10) in relapsed or refractory multiple myeloma patients treated with carfilzomib plus dexamethasone is approximately 0.30³⁰. If it becomes evident that the Grade 3/4/5 AESI rate convincingly exceeds 0.30, the study will be halted. Enrollment will be suspended if the posterior probability of the Grade 3/4/5 AESI rate exceeding 0.30 is 0.75 or higher. The prior distribution for this monitoring rule is beta (3,7). This means that our prior assumption regarding the proportion of Grade 3/4/5 AESI's is 0.30, and there is 90% probability that this proportion is between 0.098 and 0.550. The operating characteristics of the stopping rule are given in the following table and are based on 5000 simulations.

Operating Characteristics of the Stopping Rule

Number of Subjects with an AESI	Number of Treated Subjects	Posterior Probability: Pr(AESI Rate>0.30 Data)
3	5	0.781
4	8	0.779
5	11	0.761
6	14	0.777

7	17	0.767
8	20	0.768
9	23	0.772
10	26	0.770
11	29	0.761

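### Table of Events footnote f lets a pre-treatment screening scan satisfy the End of Treatment LVEF, so some early stoppers may have no post-baseline ejection fraction

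*Combined protocol and SAP*

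**What the plan says.** Footnote f of the Table of Events (18.5) sets the times at which LVEF is measured: "Echocardiogram, MUGA, or cardiac MRI to be performed at baseline, every 2 cycles (within 5 days of Day 1), and end of therapy to calculate". The on-treatment entry in the table itself is "X (prior to every 2 cycles"). Neither says which cycles are meant.

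The same footnote requires an LVEF evaluation in any subject who develops signs or symptoms of congestive heart failure at any time on study. It then closes with the waiver: "If echocardiogram, MUGA, or cardiac MRI is done within 2 months from End of Treatment visit, it does not need to be repeated".

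Three other provisions set the dates:
- Section 8.3: "All screening procedures must be completed within 21 days prior to start of study treatment".
- Footnote q: "End of Treatment visit should be completed within 30 days of last dose of study drug", or before subsequent therapy if that comes first.
- Section 8.5: if the decision to stop is made at a scheduled visit, the EOT visit takes the place of that visit.

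On the analysis side, 13.2.10 lists ejection fraction as a safety endpoint, and 13.4.3 says that "ECHO/MUGA/cardiac MRI (ejection fraction (%)) will be summarized with descriptive statistics". Neither section says how subjects without a post-baseline value are counted or reported.

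**The concern.** The purpose of an EOT ejection fraction is to record cardiac function after exposure. For a subject who stops before the first on-treatment scan, it is the only scheduled post-baseline LVEF. Read literally, footnote f lets the pre-treatment scan stand in for it, so the baseline value would serve as both baseline and end-of-treatment value.

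Other waivers in the same table are limited to a time point. Footnote s separates Cycle 1 Day 1 after screening from Cycle 1 Day 1 after crossover, and footnote j restricts its bone marrow waiver to screening. Footnote f has no such limit.

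What is at stake is decline without symptoms. Section 6.3 lists "decreased left ventricular function" separately from congestive heart failure, so the protocol treats it as a toxicity in its own right. Section 4.3 also allows a Phase I subject without a DLT who stops on Cycle 1 Day 25 or later to be DLT evaluable if the other criteria are met. Such a subject could count toward the MTD without a post-baseline ejection fraction.

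**Working it through.** The plan states no figure for LVEF completeness, so there is none to reproduce. The check is a day count.

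**Inputs.** First dose is Day 1 and there is no Day 0. The screening scan falls on Day -21 to Day -1 (8.3, 18.5). A cycle is 28 days. EOT falls between the last dose and 30 days later (footnote q). I take 2 months as 60 days and vary it from 56 to 62.

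**Formula.** Age of a scan done on Day -s at an EOT visit on Day e = (e - 1) + s.

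**Stop at the Cycle 2 Day 1 visit, EOT about Day 29.**
- Day -21 scan: 28 + 21 = 49 days.
- Day -1 scan: 28 + 1 = 29 days.

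Every allowed screening date is inside 2 months, so the EOT scan is waived whichever date was used.

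**Latest EOT day that the waiver covers.** Setting (e - 1) + s = 60 gives e = 61 - s.

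| Screening scan | 60-day window | 56 to 62 days |
|---|---|---|
| Day -21 | Day 40 | Day 36 to 42 |
| Day -14 | Day 47 | Day 43 to 49 |
| Day -7 | Day 54 | Day 50 to 56 |
| Day -1 | Day 60 | Day 56 to 62 |

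**Effect of EOT timing.**
- Last dose Day 16, EOT Day 16 to 46: a Day -21 scan is 36 to 66 days old and a Day -1 scan 16 to 46.
- Last dose Day 28, EOT Day 28 to 58: the ages are 48 to 78 and 28 to 58 days.

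With an early screening scan and a late EOT visit, the EOT scan is therefore still required.

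**First on-treatment scan.** If it precedes Cycle 3, it falls at Day 57 ± 5, that is Day 52 to 62, too late for these subjects. If it precedes Cycle 2, it falls at Day 29 ± 5, that is Day 24 to 34, and subjects who reach it are covered.

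**Run-in non-responders.** Ruxolitinib starts at about Day 29 and its first cycle ends at about Day 56, so EOT falls on Day 56 to 86. A Day -21 scan is then 76 to 106 days old (not waived), and a Day -1 scan 56 to 86 (waived only if EOT is prompt). This group is less exposed to the gap.

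**Rough scale, by assumption.** Take exponential progression, 1 - 0.5^(t/median), with the medians of 2 and 4 months in 13.1.2 and 30.4375 days per month.
- By Day 28: 1 - 0.5^(28/60.875) = 0.273, and 1 - 0.5^(28/121.75) = 0.147. That is about 8 or 4 of 30 if all 30 started ruxolitinib directly.
- By Day 40: 0.366 and 0.204, about 11 or 6 of 30.

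**The case against.** The strongest reply is that the gap is narrow and the waiver is an ordinary way to limit burden. Most of this stands.

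- Subjects with signs or symptoms of heart failure must be scanned, so symptomatic cardiac toxicity is captured. Heart failure is also a Phase II adverse event of special interest, and adverse events are recorded to 30 days after the last dose.
- The waiver is optional and expires with the age of the screening scan.
- The text does not rule out scans before Cycles 2, 4 and 6, which would cover anyone who reaches the pre-Cycle 2 scan.
- After ruxolitinib starts, footnote u does not require response results before Day 1 dosing. A subject who progresses by Day 28 may be dosed in Cycle 2 first, which delays EOT and may carry it past the window.
- The section 6.3 row governs carfilzomib during treatment. An EOT scan in a subject who has already stopped does not inform that decision.

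BNP is a weaker answer. It is scheduled on Day 1 of each cycle with no EOT entry in the table as it reads, so a subject who stops within Cycle 1 has only the Cycle 1 Day 1 value.

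A reader might infer that the LVEF summary describes only subjects who stayed on treatment, or that it understates decline. The documents support neither. Some early stoppers will be scanned, for symptoms or because the waiver has lapsed. The sign of any bias would depend on whether unscanned early stoppers have lower ejection fractions than the rest, and nothing in the documents settles that.

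**Conclusion.** The point holds in a limited form, as a minor improvement. Footnote f allows a subject without signs or symptoms of heart failure, who stops during or soon after Cycle 1, to leave without a post-baseline value for a named safety endpoint. At an EOT visit near Day 29 this is true for every permitted screening date. The descriptive summary in 13.4.3 may then under-represent early stoppers, and the plan does not ask for the number missing.

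The size is not known. The 27% and 15% are assumed progression rates by Day 28 and should not be read as rates of missing LVEF. They are rough upper guides for progression stops among subjects who start ruxolitinib directly (Phase I and those who bypass the run-in). Stops for toxicity would add to them. The documents do not say how many Phase II subjects will bypass the run-in, and 27% uses the median assumed for retreatment without ruxolitinib.

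The conclusion rests on the literal reading of footnote f and on 2 months being about 60 days. For subjects who reach Cycle 2, it also rests on the first on-treatment scan not preceding that cycle. The primary endpoint, the sample size and the stopping rule for adverse events of special interest are unaffected.

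**What to change.** Reconcile footnote f with the scheduled end-of-therapy LVEF and the ejection-fraction endpoint in 13.2.10:

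1. In footnote f, specify that only a scan done after the first dose of study treatment counts toward the 2-month EOT waiver.
2. In footnote f and the table entry, state which cycles the 2-cycle scans precede.
3. In 13.4.3, report the number of subjects with and without a post-baseline LVEF beside the descriptive summary.

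The cost is a phrase in footnote f, a clarification of the scan cycles and one reported count. The EOT scan is already in the schedule, so no new procedure is added. The downside is that a few early stoppers have a scan that they could otherwise have skipped. No dosing or treatment rule changes.

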1.3 Exploratory Objectives

Exploratory objectives include the following:

- Explore the correlation of serum cytokine profile with toxicities and treatment response
- Explore the correlation of PBMC proteasome and JAK inhibition with toxicities and treatment response
- Examine changes in biology of BM and BM plasma cells before and after treatment by RNA sequencing

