8.3.1 Disease assessments: Baseline measurements

- Bone marrow aspirate and serum for disease assessment and correlative studies: for % plasma cells, morphology, standard karyotype, cytogenetics by FISH and biomarkers
- Correlative bone marrow specimen: minimum of 12 mL of bone marrow aspirate will be collected and sent to the LCI HOT lab.
- Response assessments, including serum or urine protein electrophoresis (SPEP/UPEP), serum and Urine immunofixation (IFE), serum free light chains (SFLC)/ratio
- β 2 microglobulin
- Radiologic imaging of plasmacytoma as clinically indicated (same technique to be used throughout the trial). Positron emission tomography/computed tomography (PET/CT) scan or magnetic resonance imaging (MRI) as clinically indicated
- Bone skeletal survey

Please note that for subjects in Phase II/Run-In who cross over to Phase II/Ruxolitinib, a new baseline should be established for disease assessments prior to initiating ruxolitinib. Response to treatment with ruxolitinib will be calculated using this new baseline.

8.3.2 Screening Laboratory assessments:

- Hematology - hemoglobin, WBC with differential, and platelet count
- Coagulation - PT/INR
- Blood chemistries - sodium, chloride, potassium, magnesium, phosphate, uric acid, BUN, glucose (fasting at baseline), ALT/AST (SGPT/SGOT), alkaline phosphatase, total protein, total bilirubin, albumin, serum creatinine and estimated creatinine clearance (see Appendix 18.4), calcium and lactate dehydrogenase (LDH). Viral hepatitis panel including HBsAg, HB core antibody, HB surface antibody, HepC antibody and HIV at baseline only.
 - HBV DNA testing (by PCR): only for subjects positive for Anti-HBc or Anti-HBs
- Disease specific laboratory evaluations as noted above.
- Correlative blood specimen

8.4 On Study Procedures:

- Vital signs
- Physical Exam
- Laboratory assessments
- ECOG performance status
- Concomitant medications and procedures
- Adverse event monitoring
- ECHO, MUGA, or cardiac MRI
- Correlative studies (Blood and bone marrow aspirate)

- Note: Post-baseline correlative samples should only be collected on subjects receiving ruxolitinib (Phase I and Phase II/Ruxolitinib).

8.4.1 Disease assessments:

- Response assessments, including serum or urine protein electrophoresis (SPEP/UPEP), serum and Urine immunofixation (IFE), serum free light chains (SFLC)/ratio
 - The following assessments will be performed at each urine disease evaluation:
 - Total protein
 - UPEP

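### Run-in subjects have no correlative sample between carfilzomib-dexamethasone and ruxolitinib, so their exploratory biomarker changes reflect the whole treatment sequence

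*Combined protocol and SAP*

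**What the plan says.** For disease measures, Section 8.3.1 states that in run-in subjects who cross over "a new baseline should be established for disease assessments prior to initiating ruxolitinib". Section 13.2 and footnotes k, m and u of the Table of Events (Section 18.5) agree.

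For correlatives, footnote l says "Blood and bone marrow samples will be collected for correlatives prior to study treatment initiation". Section 4.1 dates the start of Phase II treatment from carfilzomib-dexamethasone, with or without ruxolitinib, so in run-in subjects this baseline comes before the run-in. Section 13.4.4 likewise places the baseline marrow at screening. Footnote l then adds that "ruxolitinib must have been initiated to collect correlative samples post-baseline" and, for the run-in itself, "do not collect post-baseline correlative samples on subjects receiving study treatment in Phase II/Run-In period". Section 8.4 repeats the rule: "Post-baseline correlative samples should only be collected on subjects receiving ruxolitinib".

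The later correlative samples are blood on Day 8 and blood plus marrow on Days 20-27 of ruxolitinib Cycle 1, and again at relapse or progression after ruxolitinib has begun. The marrow objective in Section 1.3 is to "Examine changes in biology of BM and BM plasma cells before and after treatment by RNA sequencing". Section 13.4.4 relates baseline cytokines, JAK inhibition and proteasome inhibition to response and toxicity, with no term or stratum for run-in exposure.

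**The concern.** Under Table 2, footnote a, every Phase II subject starts in the run-in unless prior carfilzomib reached at least 56 mg/m². A crossover subject's correlative baseline and first follow-up sample therefore sit on either side of one or more cycles of carfilzomib-dexamethasone. In Phase I and direct-entry subjects no study treatment comes between the baseline and the first ruxolitinib dose. Pooling the two groups mixes two kinds of before-and-after difference. The mixing is not random, because entry to the run-in depends on prior carfilzomib dose and its length depends on early response.

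One assay is directly exposed. Footnote l includes PBMC proteasome inhibition, and Section 2.2.2 describes carfilzomib as an irreversible proteasome inhibitor.

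What is at stake is the interpretation of the exploratory biomarker work. A pre-ruxolitinib sample that was not drawn cannot be recovered later.

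**Working it through.** The plan states no figure on this point, so the check is a reading of the text and a timing calculation.

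**Could the text already allow the missing sample?** Footnote l says "baseline samples may be collected during screening or pre-treatment on C1D1", and cycle numbers restart at ruxolitinib. One might therefore read C1D1 as ruxolitinib C1D1. Three statements rule this out: the baseline precedes study treatment (footnote l with Section 4.1), anything after baseline requires ruxolitinib to have started (footnote l, Section 8.4), and Section 13.4.4 puts the baseline marrow at screening. Footnote j does call for a later marrow ("Repeat for % plasma cells at the time of CR and/or progression"), but that is for plasma-cell percentage, and the table makes it conditional on clinical indication.

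**Timing.** Inputs:
- 28-day cycles, with six scheduled carfilzomib days per cycle (Tables 2 and 3)
- samples on Day 8 and Days 20-27 of ruxolitinib Cycle 1 (footnote l, Section 13.4.4)
- one run-in cycle for non-responders, and continuation to progression for responders (Section 4.2.2)

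Let k be the number of run-in cycles and d the sample day. With the first study dose at time 0 and no delays or visit windows:

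days from first study dose = 28k + (d − 1)

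| Subject | k | Days without ruxolitinib | Scheduled carfilzomib doses before ruxolitinib | Day 8 blood | Day 20-27 blood and marrow |
|---|---|---|---|---|---|
| Phase I or direct entry | 0 | 0 | 0 | 7 | 19-26 |
| Run-in non-responder | 1 | 28 | 6 | 35 | 47-54 |
| Run-in responder (assumed) | 2 | 56 | 12 | 63 | 75-82 |
| Run-in responder (assumed) | 3 | 84 | 18 | 91 | 103-110 |
| Run-in responder (assumed) | 6 | 168 | 36 | 175 | 187-194 |

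For the non-responder, 28/54 = 52% and 28/47 = 60% of the interval to the first follow-up marrow is without ruxolitinib. For the Day 8 blood it is 28/35 = 80%. The responder rows only illustrate a range, because the documents give neither a run-in duration for responders nor the share of subjects entering the run-in. The doses are counts of scheduled infusions, not amounts: Table 2, footnote c gives some subjects a lower dose on the first two days.

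**Clock of the outcomes.** PFS4, PFS, OS and response all run from ruxolitinib start (Sections 13.2.2 to 13.2.5). In a crossover subject the baseline covariate is therefore at least 28k days old at time zero. The screening window can add up to 21 days in either group (more if screening is extended), so the extra 28 days per run-in cycle is what separates them.

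**The case against.** The strongest reply is that the plan does not promise a ruxolitinib-specific change. The marrow objective refers to treatment, and Section 13.4.4 gives the purpose of the genomic work as understanding carfilzomib sensitivity and resistance, for which a sample before on-study carfilzomib is the right reference. The listed blood analyses use baseline values, not changes, and a baseline drawn before the outcome clock is still a legitimate predictor. The sampling restriction is repeated in several places and looks deliberate. All of this stands. It limits the point to interpretation and to a missed opportunity, and it is why the pre-study sample should be kept.

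It does not remove the difficulty with pooling: the plan neither separates nor adjusts for run-in exposure. Section 13.1.2 describes the study as examining what ruxolitinib adds to carfilzomib-dexamethasone, and run-in crossovers are the only subjects in whom a sample on the doublet, just before ruxolitinib, could bear on that.

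Three stronger inferences are tempting and unsupported:
- **That Phase I and direct-entry subjects show the ruxolitinib effect.** They start all three drugs together (Tables 1 and 3), so their change is a three-drug effect.
- **That the new sample should become the baseline in Section 13.4.4.** The covariate would then be an on-treatment value in crossovers and a pre-treatment value in everyone else, which is a new non-random mismatch. It would also discard the pre-carfilzomib reference for proteasome inhibition.
- **That efficacy results are compromised.** Disease measures are re-baselined, so they are not.

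**Conclusion.** The point holds for exploratory biomarker analyses in Phase II run-in crossovers. Their correlative changes are effects of the whole treatment sequence, with at least 28 of 47-54 days before the first follow-up marrow spent without ruxolitinib. Their baseline covariates precede the outcome clock by one or more cycles. This assumes 28-day cycles without delays. The number of subjects affected and the length of the run-in in responders cannot be derived from the documents. PFS4, the two-stage rule and the secondary endpoints are untouched, so this is a worthwhile and inexpensive improvement, not a threat to the trial's validity.

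**What to change.** 1. Amend footnote l and Section 8.4 to collect one additional correlative blood set (about 28 mL, as already specified) before the first ruxolitinib dose in every run-in crossover. Footnote s does not let these subjects rely on screening results for ruxolitinib C1D1, so hematology and chemistry draws are already due then. Use this set as the reference for change after ruxolitinib is added in those subjects.
2. Keep the pre-study sample as the pre-carfilzomib reference, including for proteasome inhibition.
3. In Section 13.4.4, report or stratify biomarker analyses by run-in versus no run-in. Describe changes in Phase I and direct-entry subjects as three-drug effects, and run-in marrow changes as effects of the whole sequence.
4. Add no marrow procedure. Where an aspirate is done anyway at run-in progression, correlative material may be banked if volume allows. This may often fail, since the aspirate is conditional and footnote l asks for at least 12 mL. Non-responders who have not progressed would still have no pre-ruxolitinib marrow.

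The new sample narrows the attribution problem without fully solving it. Without delays, it falls 29 − 16 = 13 days after the last run-in carfilzomib dose. The Day 8 pre-dose blood falls 8 − 2 = 6 days after the last dose, and the Day 20-27 sample 4-11 days after. The analysis text should acknowledge this.

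The cost is the extra blood volume, the assays, the amended wording, and smaller subgroups in an already exploratory analysis.
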